8.2.2. Analysis for Primary Endpoint

The primary endpoint is DCR, which is defined as the proportion of patients with a documented complete response (CR), partial response (PR), and stable disease (SD). The categorization of response (CR, PR, SD, PD, and NE) and the derivations of BOR are provided in Appendix 1.1.

DCR will be summarized by arm and sub-cohort for the response evaluable set. DCR point estimates will be provided along with the corresponding 2-sided 95% confidence intervals using an exact method [1]. Sensitivity analysis of DCR will be performed for all patients in the safety set.

8.2.3. Analysis for Secondary Endpoints

8.2.3.1. PK Analysis

Nuventra Pharma Sciences will compute PK parameters by noncompartmental analysis using Phoenix WinNonlin version 8.1 (Certara, Princeton, NJ), and generate TLFs using a validated version of R version 3.4.0 or later (R Foundation for Statistical Computing, Vienna, Austria).

Demographics for patients included in the PK Analysis Set will be summarized in the PK report, summarized by arm and cohort.

8.2.3.1.1. PK Concentrations

Plasma concentrations will be listed and summarized by napabucasin dose, concomitant treatment, and nominal timepoint using descriptive statistics, including N, mean, standard deviation, coefficient of variation (CV), minimum, maximum, and median.

Figures of individual and mean drug concentrations vs actual or nominal elapsed time will be presented on linear and semi logarithmic scales by day, napabucasin dose, and concomitant therapy, as appropriate.

8.2.3.1.2. Pharmacokinetic parameters

PK parameters for napabucasin, including maximum concentration at steady state (Cmax,ss), the timepoint when Cmax was observed (Tmax), area under the plasma concentration time curve during a dosing interval at steady state (AUCtau), minimum concentration at steady state (Cmin,ss), total body clearance at steady state (CLss/F), volume of distribution during terminal elimination phase at steady state (Vz/F), and terminal elimination half-life (t1/2) will be listed and summarized using descriptive statistics, including N, mean, standard deviation, CV, geometric mean, geometric CV, minimum, maximum, and median. For Tmax, N, minimum, maximum, and median will be reported. Parameters will be summarized by day, napabucasin dose, concomitant therapy and cohort.

PK parameters for capecitabine and metabolite 5-FU, including maximum concentration after a single dose (Cmax), the timepoint when Cmax was observed (Tmax), area under the plasma concentration time curve from zero to the last quantifiable concentration (AUClast), area under the plasma concentration time curve from zero extrapolated to infinity (AUCinf), total body clearance (CL/F) volume of distribution during the terminal elimination phase (Vz/F), and t½, will be listed and summarized using descriptive statistics, including N, mean, standard deviation, CV, geometric mean, geometric CV, minimum, maximum, and median. For Tmax, N, minimum, maximum, and median will be reported. Parameters will be summarized by day and napabucasin dose.

Napabucasin PK parameters will be estimated using actual elapsed time from napabucasin dosing. PK parameters of capecitabine and metabolite 5-FU will be estimated using actual elapsed time from capecitabine dosing. Imputation of concentration data for BLQ is described in Section 7.5.

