# 5.3.3.4 Week 4 (Cycle 1, Day 21)

The following assessments will be made during this visit:

- Karnofsky performance status
- Vital signs (weight, pulse)
- Hematology (see Section 6.3)
- Blood chemistry (see Section 6.3)
- Liver function tests (see Section 6.3)
- Electrolytes (see Section 6.3)
- Urinalysis (see Section 6.3)
- Assess AEs
- Record concomitant medication
- The second dose of BBI608 will be given approximately 12 hours after the first dose.
- Blood samples for pharmacokinetics, (for only the first six patients enrolled in this arm.)
- Dispense BBI608 (1 week supply)

Blood samples for pharmacokinetics will be collected immediately prior to the first dose of BBI608 and will continue through 24 hours after administration of the first dose of BBI608. Specific details for the collection of blood samples for pharmacokinetics can be located in Sections 6.4 and Section 16.

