## 7.1.3 Cetuximab, Panitumumab, or Capecitabine Administration

- Detailed instructions for the preparation, premedication, and administration of Cetuximab, Panitumumab, or Capecitabine are provided in the Product Labels approved by Health Canada or US FDA.
- Cetuximab will be administered via IV on Days 5, 12, 19 and 26 of a 28 day cycle, about 3 hours after the first daily dose of BBI608. Panitumumab will be administered via IV on Days 8, and 22 of a 28 day cycle, about 3 hours after the first daily dose of BBI608. Capecitabine will be administered orally twice-daily for two weeks out of three weeks. The first dose of Capecitabine should be taken about 3 hours after the first daily dose of BBI608 on day 8 of each 3 week cycle of Capecitabine.

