7.5. Pharmacokinetics

For individual concentration-time plots and the calculation of PK parameters using noncompartmental analysis, individual below the limit of quantification (BLQ) values will be converted using the following rules:

- If a BLQ value occurs in a profile before the first quantifiable concentration, it will be assigned a value of zero.
- If a BLQ value occurs after a quantifiable concentration in a profile and is immediately followed by a value above the lower limit of quantification (LLQ), then the BLQ value should be treated as missing.
- If a BLQ value occurs at the end of the collection interval (after the last quantifiable concentration) it will be treated as missing.

• If two BLQ values occur in succession after Cmax, the profile will be deemed to have terminated at the first BLQ value and any subsequent quantifiable concentrations will be omitted from PK calculations by treating them as missing.

When imputing BLQ concentrations for the generation of summary statistics at a given time point, all BLQ values will be set to zero except when an individual BLQ falls between two quantifiable values, in which case it will be treated as missing. These same imputations apply to imputation of BLQ concentrations used for generation of concentration-time profiles based on summary statistics.

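### SAP 8.2.3.1.2 applies one single-dose parameter list to capecitabine and 5-FU on both PK days; it does not fit 5-FU clearance, the 24 h sample or Day 21

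*SAP*

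**What the plan says.** SAP 8.2.3.1.2 gives parent and metabolite a joint list: "PK parameters for capecitabine and metabolite 5-FU, including maximum concentration after a single dose (Cmax"), Tmax, "area under the plasma concentration time curve from zero to the last quantifiable concentration (AUClast"), AUCinf, and "total body clearance (CL/F) volume of distribution during the terminal elimination phase (Vz/F), and t½". Nothing limits CL/F and Vz/F to the parent. The list is summarized by day, so it covers both Arm C sampling occasions (Days 8-9 and 21-22). The time origin is common to both analytes: "PK parameters of capecitabine and metabolite 5-FU will be estimated using actual elapsed time from capecitabine dosing".

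On dosing, Protocol 7.1.3 states "Capecitabine will be administered orally twice-daily for two weeks out of three weeks", and Protocol 4.1 places those doses on Days 8 to 21. SAP 3.2 names 5-FU only as a metabolite. Protocol Appendix D gives capecitabine at 175 min after BBI608 (napabucasin), takes nine samples from 180 to 660 min, and takes one more at 24 h.

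SAP 7.5 shortens a profile only for values below quantification (BLQ): "If a BLQ value occurs at the end of the collection interval (after the last quantifiable concentration) it will be treated as missing", and two successive BLQ values after Cmax end it. Neither document says that the evening capecitabine dose is held on PK days, or that the 24 h sample is left out of the capecitabine and 5-FU noncompartmental analysis (NCA).

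**The concern.** Each parameter in the list carries a condition. CL/F and Vz/F need a known dose of the analyte. A terminal half-life needs points from the decline of one dose. AUCinf as a measure of that dose's exposure, and dose/AUCinf as clearance, need a single dose. The first condition fails for 5-FU. The second fails when a sample taken after the evening dose enters the profile. The third fails on Day 21.

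The tables at stake answer the first secondary objective, the PK profile of the combination. With six patients sampled in the arm, a few distorted half-lives or clearances would dominate a summary. If the plan gives no cut-off, the analyst chooses one after seeing the concentrations.

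**Working it through.** The documents give no PK target figure to reproduce. The check uses Appendix D sampling times, the dosing schedule and one illustrative model.

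**1. 5-FU clearance.** CL/F = dose/AUC and Vz/F = dose/(λz × AUC). The only dose available is capecitabine's. In molar terms, dose(capecitabine)/AUC(5-FU) = CL(5-FU)/(F × fm), where fm is the fraction converted to 5-FU. The plan does not measure fm. If fm were 0.8 to 0.2 (an assumption, only to show scale), the value would be 1/0.8 = 1.25 to 1/0.2 = 5 times the CL/F that would otherwise be reported. Using milligrams without a molar conversion adds a further factor.

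**2. Where the 24 h sample falls.**
- Hours after the morning capecitabine dose, (t − 175)/60: 0.08, 1.08, … 8.08 for the nine samples to 660 min, then (1440 − 175)/60 = 21.08.
- Second dose, if 12 h later (assumption): 175 + 720 = 895 min.
- The 24 h sample is then (1440 − 895)/60 = 9.08 h after dose 2. With spacing of 14 to 10 h, it is 7.1 to 11.1 h after dose 2.
- So nine of ten post-dose samples precede dose 2. They cover 8.08/12 = 67% of the interval.

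**3. Effect of keeping the 24 h sample.** The model is one-compartment and noiseless, with ka = 2/h assumed and k = ln 2/half-life. For the first dose, C(t) = ka/(ka − k) × [exp(−kt) − exp(−ka·t)]; the same term in (t − 12) is added after 12 h. True AUCinf is 1/k. AUC is linear-up/log-down, and λz comes from the last three points (7.08, 8.08 and 21.08 h).

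| True half-life (h) | Half-life read | AUCinf/true, 24 h kept | AUCinf/true, stopped at 660 min |
|---|---|---|---|
| 1 | 8.7 | 0.95 | 0.90 |
| 2 | 17.9 | 1.63 | 0.95 |
| 3 | 31 | 2.82 | 0.97 |

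Stopping at 660 min returns the true half-life in each row. Linear trapezoids change the third column only to 0.97, 1.64 and 2.82.

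Derived parameters follow. CL/F is off by 1/0.95 = 1.05, 1/1.63 = 0.61 and 1/2.82 = 0.35. Vz/F is off by the half-life ratio over the AUCinf ratio: 8.7/0.95 = 9.2, (17.9/2)/1.63 = 5.5 and (31/3)/2.82 = 3.7. At 1 h AUCinf and CL/F are unharmed, but half-life and Vz/F are not.

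**4. Day 21.** Days 8 to 20 are 13 days × 2 = 26 doses, so the Day 21 morning dose is number 27. AUCinf after that dose includes carry-over from earlier doses, and dose/AUCinf is the wrong clearance formula. An AUC over the dosing interval (AUCtau) is listed for napabucasin but not for capecitabine.

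**The case against.** **The samples are adequate.** A reader might infer that the sampling cannot support AUClast, AUCinf or half-life. The documents do not support that. Day 8 is the first capecitabine dose, and nine samples over 8.08 h precede the second. These suffice if the terminal phase is visible by then. The fault is a missing cut-off rule, and an experienced PK analyst might truncate anyway.

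**The harm may not occur.** The documents give no half-life, absorption rate or quantification limit. In the model with a 1 h half-life, the 24 h value is about 0.5% of peak and may be BLQ. SAP 7.5 would then treat it as missing. The two-successive-BLQ rule can also end the profile earlier. This stands, so the error is conditional. It is still not excluded by any rule.

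**A 5-FU figure is not meaningless.** CL/(F × fm) can be reported as a composite apparent value. This also stands; the error lies in calling it clearance or volume.

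**Napabucasin.** A reader might extend the point to Arms A and B, where sampling on the dosing day ends at 540 min (9 h) and the 24, 27, 99 and 171 h samples follow later napabucasin doses. That reading is too strong. SAP 8.2.3.1.2 already defines napabucasin AUCtau over a steady-state dosing interval, which bounds CLss/F too. The 27, 99 and 171 h samples sit exactly 24, 96 and 168 h after the antibody infusion starts at 3 h, so they fit an antibody schedule. Only a clarifying sentence is needed.

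**The capecitabine interval.** The 12 h spacing is not stated for capecitabine. Protocol 5.3.3.4 says "The second dose of BBI608 will be given approximately 12 hours after the first dose", which concerns BBI608 only. The spacing remains an assumption, and the range of 10 to 14 h does not move the 24 h sample ahead of the second dose.

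**Conclusion.** The concern holds in three limited parts. Two need no PK assumption: CL/F and Vz/F cannot be 5-FU clearance and volume, and single-dose terms do not fit Day 21. The third is conditional: a quantifiable 24 h value distorts half-life and Vz/F and, unless the half-life is short, AUCinf and CL/F. The sizes in the table rest on the assumed one-compartment model, ka of 2/h, half-lives of 1 to 3 h and 12 h spacing. They illustrate the effect and do not predict it.

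Severity is minor. The affected tables are descriptive secondary PK in the first six patients of the capecitabine arm. SAP 4.1 plans no hypothesis testing, and no decision rule in SAP 4.2 uses PK. The primary endpoint is untouched.

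**What to change.** In SAP 8.2.3.1.2:

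- **5-FU:** delete CL/F and Vz/F, or label them as apparent composite values based on the capecitabine dose. Report Cmax, Tmax, AUC, half-life and the molar 5-FU to capecitabine AUC ratio.
- **Cut-off:** end capecitabine and 5-FU NCA profiles at the next capecitabine dose, using samples to 660 min. List the 24 h sample as a concentration only.
- **Day 21:** keep single-dose terms for Day 8. On Day 21 report capecitabine AUCtau and CL/F = dose/AUCtau. Extend from 8.08 to 12 h with λz, and report the extrapolated share. In the same model at steady state, that stretch holds about 6 to 11% of AUCtau at half-lives of 2 to 3 h.
- **Napabucasin:** add that parameters use samples before the next napabucasin dose (to 540 min in Arms A and B, 660 min in Arm C), with the 12 h value set to the pre-dose concentration for AUCtau.

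The cost is SAP wording and NCA settings, with no new samples and no change to dosing. The downside is that the capecitabine 12 h value is extrapolated and the napabucasin 12 h value assumes steady state, which the SAP's napabucasin parameter names already do.

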8.2.3.2. PD/Biomarker Analysis

Tumor archival tissues and biopsies will be collected as described in the protocol amendment 2 [5] Section 6.5. A listing of tumor biomarkers may be provided if data are available.

Additional analyses of safety and/or efficacy may be performed in subsets defined by biomarker status as determined by evaluation of archival tissue.

8.2.3.3. Other Efficacy Endpoints Analysis

Summary tables of Objective Response Rate (ORR), Progression Free Survival (PFS), and Overall Survival (OS) will be provided by arm and sub-cohort. The ORR will be summarized for the response evaluable set and safety set. The PFS and OS will be summarized with KM method for all patients in the safety set with start day calculated from the date of first treatment. Sensitivity analysis may be considered for PFS and OS based on the FAS with start day calculated from the date of patient enrollment if data are available. KM analysis will not be conducted if the number of events is less than 5.

Efficacy listings to be provided include best response, first CR/PR date, last date with CR or PR, most recent date without progression, progression date, death date, date of first response and last tumor assessment date, etc. Swimmer plots for individual response and time on treatment, waterfall plots for individual tumor size percent change from baseline, and spider plots for individual tumor size percent change from baseline.

Endpoint	Analysis Set	Statistical Method	Missing Data
Response (DCR, ORR, CR, PR)	Efficacy	Exact CI	Observed case
Overall Survival (OS)	Efficacy	Kaplan-Meier	Censored at date of last contact (Appendix 1.3)
Progression Free Survival (PFS)	Efficacy	Kaplan-Meier	Censored per Table A.1.3.1 (Appendix 1.3)
Overall Survival and PFS follow-up time)	Efficacy	Reverse Kaplan- Meier	Event and censor in the original KM analysis are reversed.

The following table provides an overview of the efficacy analysis.

8.2.3.4. DLT

A listing of the DLTs will be provided by arm and cohort.

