DLT occurs in  $\geq 2$  of the 6 patients in a combination arm, then that arm of the study will be closed and no further patients will be enrolled. A given arm of the study of BBI608 in combination with Cetuximab, or Panitumumab, or Capecitabine will continue to enroll patients if no more than 1 out of 6 patients in the combination arm has an observable DLT.

Number of Subjects with DLT at 480 mg bid BBI608	DLT Decision Rule
≤ 1 out of 6	Continue patient enrollment in combination arm
≥2 out of 6	Close combination arm of the study

The following number of colorectal cancer patients will be enrolled based on a two-stage Simon design with an alpha of 5% and a power of 80% to detect a disease control rate improvement for Cetuximab and Panitumumab from about 30% (historical DCR for 3rd and 4th line colorectal cancer) to 60%, and a disease control rate improvement for Capecitabine from about 15% (historical DCR for 3rd line colorectal cancer) to 60%.

Table 1 Simon two-stage design for Phase II

	Patient number				
Combo Therapy	Stage 1	Stage 2	Total*		
Cetuximab	8	16	24		
Panitumumab	8	16	24		
Capecitabine	6	12	18		

\*If any of the three arms reach a DCR of 60% or more at the end of Simon Stage 2, a one-time option to expand accrual to a total sample size of up to 50 patients may be implemented for each arm.

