# 4.5 Dose-Limiting Toxicity

Dose-limiting toxicity is defined by the occurrence of any of the following toxicities possibly or probably related to BBI608 in combination with Cetuximab, or Panitumumab or Capecitabine within 28 days of treatment. DLT will be scored during the 28 days of BBI608 treatment.

- Grade 4 hematological toxicity
- Grade 3 or 4 non-hematological toxicity, except:
  - o Grade 3 or 4 nausea/vomiting/anorexia, diarrhea and fatigue will be considered a DLT only if it persists more than three (3) days despite optimal medical management
  - o Alopecia will not be considered a DLT

Adverse events considered related to Cetuximab, or Panitumumab or Capecitabine will not be considered DLTs.

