### 10.7 Safety Analysis

Safety will be assessed by physical examination, and laboratory assessments. Adverse events will be graded according to the NCI CTCAE, version 4.0. The incidence of adverse events and DLTs will be evaluated for each combination arm, and for all patients combined. Patients will be followed for adverse events for at least 30 days after the last dose of BBI608, or until recovered from all related BBI608 adverse events.

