2.1. Study Design

This is an open label, multi-center, Phase II study of napabucasin (BBI608) administered in combination with either cetuximab, or panitumumab, or capecitabine to patients with advanced colorectal cancer. The study is designed to explore the safety, tolerability, preliminary anti-tumor activity and pharmacokinetics of napabucasin when administered in combination with each one of the above regimens.

Six patients would be initially enrolled in each combination arm at a napabucasin dose level of 500 mg BID (1000 mg total daily using 50 mg capsules) before protocol amendment 2 or 480 mg twice daily (960 mg total daily dose) using 80 mg capsules after protocol amendment 2. If ≤ 1 out of 6 patients had an observable dose limiting toxicity (DLT) in the combination regimen, then that arm of the study would continue to enroll patients at 500 mg BID (1000 mg total daily) using 50 mg capsules or 480 mg BID (960 mg total daily) using 80 mg capsules following a Simon 2-stage design. If a DLT occurred in ≥ 2 of the 6 patients in a combination arm, then that arm of the study would be closed and no further patients would be enrolled. A given arm of napabucasin in combination with cetuximab, or panitumumab, or capecitabine would continue to enroll patients if no more than 1 out of 6 patients in the combination arm had an observable DLT.

The number of colorectal cancer patients enrolled would be based on a two-stage Simon design and is presented in Section 4.1 of the protocol amendment 2 [5]. If any of the three arms reach a disease control rate (DCR) of 60% or higher at the end of the Simon Stage 2 portion of the study, a one-time option to expand accrual to a total sample size of up to 50 patients may be implemented for each arm.

To evaluate the tolerability of napabucasin, patients from each arm would be assigned to one of 4 sub-cohorts (with 6 patients in each sub-cohort: IA, IB, IIA, IIB) from protocol amendment 2. The evaluation of tolerability would be done at selected centers for the study arm that was continuing patient accrual and in which a total of 50 evaluable patients had not been reached. For each

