2.2 Study Objectives

2.1.1. Primary Objectives

To determine the safety and preliminary anti-tumor activity of napabucasin when administered in combination with cetuximab, or panitumumab, or capecitabine in adult patients with advanced colorectal cancer who have failed first- and second-line treatment.

The primary endpoint is disease control rate, defined as the proportion of patients with a documented complete response, partial response and stable disease (CR + PR + SD) based on

RECIST 1.1. The secondary endpoints include progression-free survival (PFS) and overall survival (OS).

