4.2. Statistical Decision Rules

4.2.1. DLT Decision Rule

DLT decisions are based on the observed number of patients with DLT at 480 mg BID napabucasin.

Number of Patients with DLT at 480 mg bid	DLT Decision Rule	
≤ 1 out of 6	Continue patient enrollment in combination arm	
\geq 2 out of 6	Close combination arm of the study	

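### The SAP reduces the DLT incidence promised in the protocol to a listing, so no DLT rate with a denominator and interval is specified for any arm

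*SAP*

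**What the plan says.** Safety is half of the primary objective: "To determine the safety and preliminary anti-tumor activity of napabucasin when administered in combination with cetuximab, or panitumumab, or capecitabine" (SAP 2.1.1). The named primary endpoint is disease control rate, and SAP 3.2 places DLT among the secondary endpoints.

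Protocol 10.7 states the DLT analysis: "The incidence of adverse events and DLTs will be evaluated for each combination arm, and for all patients combined". The synopsis says the same in its section on DLT criteria. SAP 8.2.3.4 is a single sentence: "A listing of the DLTs will be provided by arm and cohort". SAP 8.1.2 says that binary endpoints receive a point estimate and a two-sided exact 95% confidence interval for each arm.

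The DLT decision rule concerns enrolment. An arm "would continue to enroll patients if no more than 1 out of 6 patients in the combination arm had an observable DLT" (SAP 2.1). With two or more DLTs in six, "then that arm of the study will be closed and no further patients will be enrolled" (Protocol 4.1). Neither document gives a target DLT rate, the rule's operating characteristics or a DLT check after the sixth patient.

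On dose, SAP 4.2.1 says: "DLT decisions are based on the observed number of patients with DLT at 480 mg BID napabucasin". SAP 2.1 says: "Six patients would be initially enrolled in each combination arm at a napabucasin dose level of 500 mg BID" before protocol amendment 2, and 480 mg twice daily after it.

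**The concern.** The protocol commits to a DLT incidence, and the SAP, which governs what is programmed, specifies an output that cannot supply one. A reader of the final report would see individual DLTs but no rate, no statement of how many patients could have had one, and no measure of uncertainty. SAP section 6 defines no DLT-evaluable set, so the denominator would have to be chosen after the data are known. Protocol 11.3 allows replacement of patients who do not receive four weeks of BBI608 for reasons other than DLT, so that choice matters.

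At stake is how much the trial says about early toxicity of each combination. Without a planned rate, the only DLT figure with a fixed denominator is the count in the first six patients of an arm. That count was meant to steer accrual, and it is too small to describe toxicity. Protocol 4.5 does not restrict DLT scoring to those six ("DLT will be scored during the 28 days of BBI608 treatment"), so later patients can contribute.

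**Working it through.** **1. The texts side by side**

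| Source | DLT output |
|---|---|
| Protocol synopsis and 10.7 | Incidence, per arm and for all patients |
| SAP 3.2 | Secondary endpoint |
| SAP 8.1.2 | Estimate and exact 95% CI for binary endpoints, by arm |
| SAP 8.2.3.4 | Listing by arm and cohort |
| SAP section 6 | No DLT-evaluable set |

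The specific instruction in 8.2.3.4 is the one a programmer will follow.

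**2. Do the adverse event tables fill the gap?** SAP 8.2.4.1 gives the number and percentage of patients with treatment-emergent events, including Grade 3 or higher, serious and drug-related events. A DLT differs in three ways (Protocol 4.5): it has a 28-day window; nausea/vomiting/anorexia, diarrhea and fatigue count only if they last more than three days despite optimal management; and events attributed to the combination drug are excluded. The treatment-emergent tables run to 30 days after the last dose, apply neither the persistence nor the attribution condition in that form, and have no stated intervals. The DLT rate cannot be read from them.

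**3. How the six-patient rule behaves.** The documents state no figure to reproduce. With true DLT rate p and independent patients,

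P(continue) = P(X ≤ 1) = (1 − p)^6 + 6p(1 − p)^5.

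The true rates below are assumptions.

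| p | (1 − p)^6 | 6p(1 − p)^5 | P(continue) |
|---|---|---|---|
| 10% | 0.531 | 0.354 | 0.886 |
| 20% | 0.262 | 0.393 | 0.655 |
| 30% | 0.118 | 0.303 | 0.420 |
| 40% | 0.047 | 0.187 | 0.233 |
| 50% | 0.016 | 0.094 | 0.109 |

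**4. Precision.** The exact (Clopper-Pearson) 95% interval for x of n runs from the 2.5% quantile of Beta(x, n − x + 1) to the 97.5% quantile of Beta(x + 1, n − x). For x = 0 the upper limit is 1 − 0.025^(1/n); with n = 6 this is 0.459.

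The documents contain no DLT data, so the counts are illustrative, at or near an observed one in six apart from the 0/6 row. The sizes 18 and 24 are the arm totals in Protocol Table 1, and 50 is the ceiling. For n = 12, I assume an arm of 24 filled by four sub-cohorts of six. IA and IB start at 240 mg twice daily, leaving 24 − 12 = 12 at the higher starting dose.

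| Count | Rate | Exact 95% CI |
|---|---|---|
| 0/6 | 0% | 0 to 45.9% |
| 1/6 | 16.7% | 0.4% to 64.1% |
| 2/12 | 16.7% | 2.1% to 48.4% |
| 3/18 | 16.7% | 3.6% to 41.4% |
| 4/24 | 16.7% | 4.7% to 37.4% |
| 8/50 | 16.0% | 7.2% to 29.1% |

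**5. Realistic arm size.** Protocol 3.3 expects 60 to 80 patients in all: 60/3 = 20 to 80/3 ≈ 27 per arm if split evenly. Fifty per arm is a ceiling on response-evaluable patients (SAP 4.3), reached in the protocol through an optional expansion.

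**6. Dose wording.** SAP 2.1 applies the six-patient rule to patients on either 500 mg or 480 mg twice daily, depending on timing. SAP 4.2.1 names 480 mg only. Read literally and alone, 4.2.1 counts nobody in an arm whose first six all received 500 mg.

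**The case against.** The strongest reply is that this is an inconsistency and not an absence. The SAP says it is to be read with the protocol, which plans the incidence. DLT is a secondary endpoint, and a literal reading of SAP 8.1.2 would give it an exact interval by arm. That is a fair description of the fault, but it does not remove it: the section written for DLTs asks only for a listing, and no denominator is defined anywhere.

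A reader might infer that the primary safety question is never answered with a rate. The documents do not support that. SAP 8.2.4.1 reports numbers and percentages across the safety set, and SAP 8.2 summarises by arm and sub-cohort. Only the DLT rate lacks a table.

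A reader might also infer that one DLT or fewer in six declares a combination tolerable. The rule only continues or closes enrolment. Tolerability of the dosing and anti-diarrheal regimens is assessed separately, through adverse event profile and achieved dose intensity. The plan sets no target DLT rate and tests no hypothesis, so the lack of a margin in the rule is not in itself an error, and calling 30% or 40% too toxic would be an outside judgement. The rule does respond to toxicity: it continues 89% of arms at a true rate of 10% and 11% at 50%.

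The gain in precision should not be oversold either. Fifty per arm is not expected, and separating starting doses gives back part of the improvement.

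On dose, SAP 2.1 largely conveys the intention. What remains is a mismatch of wording in 4.2.1.

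**Conclusion.** The point holds as a departure of the SAP from the protocol, and from its own treatment of secondary and binary endpoints. A DLT incidence promised per arm and for all patients has become a listing, with no defined denominator. The consequence is limited but real, because safety is a primary objective. The only DLT count used in a decision is the six-patient one, whose exact 95% upper limit is 64% at 1/6 and 46% at 0/6. At a similar observed rate, a planned estimate would bring that limit to about 37% to 41% with 18 to 24 patients, to 29% at the ceiling of 50, and to only 48% with 12 patients at one starting dose.

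These figures assume independent patients and illustrative counts. They also assume that the protocol's arm sizes are a fair guide; SAP 4.2.2 says the Simon design was not followed, so actual sizes may differ. The 480/500 mg wording is a smaller, separate mismatch that needs reconciling.

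**What to change.** 1. **SAP section 6:** define one DLT-evaluable set. For example, take treated patients who either had a DLT or completed the 28-day window, in line with the replacement rule in Protocol 11.3. Use this single denominator throughout.
2. **SAP 8.2.3.4:** specify number, percentage and exact 95% confidence interval of DLT-evaluable patients with a DLT, by arm, by starting dose (240 mg twice daily versus 480 or 500 mg twice daily) and for all patients combined. Keep the listing.
3. **SAP 4.2.1 and 2.1:** reconcile the dose wording, so that it is clear which patients the reported six-patient count includes.

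The cost is one table, one denominator definition and a wording correction. DLT status cannot be derived from grade and dates alone, because it needs a judgement on persistence despite management and on attribution. The listing already requires that determination for each DLT, so the numerator needs no further data collection. No added patients or visits are needed.
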